1 BACKGROUND AND RATIONALE

This document presents the statistical analysis plan (SAP) for Protocol C4951010 (BHV3000-404): A Phase 4 Randomized, Double-blind, Placebo-controlled Study to Evaluate the Efficacy and Safety of Rimegepant in Episodic Migraine Prevention with Multiple Dosing Regimens.

This SAP contains the analysis details and methodology to answer the study objectives, including planned tables, listings, and figures (TLFs), which provide the basis for the results section of the clinical study report (CSR).

This SAP also references the Rimegepant/Zavegepant Core SAP, which is hereafter referred to as the "Core SAP".

1.1 Research Hypothesis

Rimegepant 75 mg orally disintegrating tablet (ODT) is safe and effective when taken daily for the prevention of migraine.

1.2 Schedule of Analyses

There is 1 planned database lock, last subject last visit (LSLV) database lock, which occurs when the last subject completes the Follow-Up Week 8 Visit. The LSLV final CSR is produced after the LSLV database lock.

No interim analyses are planned.

2 STUDY DESCRIPTION

2.1 Study Design

This is a multicenter, randomized, double-blind, placebo-controlled study to assess the efficacy and safety of 2 different dosing regimens of rimegepant 75 mg ODT in episodic migraine prevention with an open-label extension phase.

[figure not shown]
The study has 4 phases:

- Observation Phase (OP): Lasts approximately 28 days. Includes the Screening Visit and Pre-Randomization Evaluation Visit which must occur within 4 days of the Baseline Visit.
- Double-blind Treatment (DBT) Phase:
 - Lasts up to 12 weeks, and includes the Baseline Visit, and Week 2, Week 4, Week 8,
 Week 12, and End of Treatment (EOT) Visits.
 - O Subjects are randomized 1:1:1 to one of the following 3 treatment groups at the Baseline Visit:
 - Rimegepant 75 mg dosed every other day (EOD) alternating with matching placebo
 EOD

- Rimegepant 75 mg dosed daily
- Placebo matching rimegepant 75 mg dosed daily.
- Randomization is stratified using an Interactive Web Response System (IWRS) by use of prior prophylactic migraine medication generally considered to have efficacy (yes or no). See Section 2.2.
- All randomized subjects who discontinue early from the DBT Phase should complete the EOT Visit. Otherwise, subjects should complete the Week 12 Visit.
- Open-label Extension (OLE) Phase:
 - Subjects who (1) complete the DBT Phase, (2) continue to meet all inclusion/exclusion criteria, and (3) have been compliant with the eDiary may enter the OLE Phase, pending review of laboratory test results.
 - Lasts up to 12 weeks, and includes the Week 14, Week 16, Week 20, Week 24, and EOT Visits.
 - Subjects take rimegepant 75 mg dosed daily.
 - All randomized subjects who discontinue early from the OLE Phase should complete the EOT Visit. Otherwise, subjects should complete the Week 24 Visit.
- Follow-Up Phase
 - Lasts up to 8 weeks, and includes Follow-up Week 2 and Follow-up Week 8 Visits primarily for safety assessments. These visits should occur approximately 2 weeks and 8 weeks, respectively, after the last visit in the last treatment phase (i.e., Week 12/EOT Visit if the subject did not enter the OLE Phase; Week 24/EOT Visit if the subject entered the OLE Phase).
 - o All randomized subjects should complete both follow-up visits, regardless of completing either treatment phase.

The design of the study is shown in Figure 1. Approximately 1300 subjects are enrolled in order to randomize approximately 660 subjects.

Figure 1 Study Schematic

2.2 Treatment Assignment

The IWRS assigns a subject identifier number at the Screening Visit.

The IWRS randomizes eligible subjects to treatment groups (see Section 2.1) using permuted blocks of size 6 at the Baseline Visit. Randomization is stratified by use of prior prophylactic migraine medication generally considered to have efficacy (yes or no).

The IWRS also assigns specific container numbers for study drug to be dispensed at the Baseline Visit and subsequent visits in the DBT and OLE Phases.

2.3 Blinding and Unblinding

This study is blinded to treatment group through the LSLV database lock (see Section 1.2). Draft TLFs for the LSLV final CSR are produced with dummy treatment groups prior to LSLV database lock. Final TLFs for the LSLV final CSR are produced unblinded.

2.4 Protocol and Protocol Amendments

C4951010 SAP Versions 1 and 2 are based on C4951010 Protocol Version 4 (01-Jul-2022).

C4951010 SAP Versions 3 and 4 are based on C4951010 Protocol Version 5 (26-Jun-2023). Protocol changes that affected statistical analyses were the following: changing the sponsorship to Pfizer; stating that there is 1 planned database lock; using robust standard error (SE) estimation methods; excluding subject as a random effect from linear mixed effects models; replacing Cochran-Mantel-Haenszel test with Mantel-Haenszel risk estimation; and modifying exclusion criteria, which affects relevant protocol deviations.

C4951010 SAP Version 5 is based on C4951010 Protocol Version 5 (26-Jun-2023). This SAP makes changes to definitions and categories in Sections 6.2 and 6.4 based on project-level changes to the Core SAP.

C4951010 SAP Version 6 is based on C4951010 Protocol Version 5 (26-Jun-2023) and Rimegepant/Zavegepant Core SAP Version 7 (15-Oct-2024). This SAP incorporates programlevel changes to relevant protocol deviations and certain aspects of data collection.

C4951010 SAP Version 7 is based on C4951010 Protocol Version 5 (26-Jun-2023) and Rimegepant/Zavegepant Core SAP Version 8 (21-Oct-2024). This SAP adds several tables related to hypertension AEs.

3 STUDY OBJECTIVES AND ESTIMANDS

3.1 Objectives

A month is defined as 4 weeks (28 days) for the purpose of this protocol.

3.1.1 Primary Objective

To evaluate the efficacy of EOD and daily rimegepant dosing regimens relative to placebo as a preventive treatment for episodic migraine, as measured by the mean reduction from the OP in the number of migraine days per month over the entire DBT Phase.

3.1.2 Secondary Objectives

- 1. To evaluate the proportion of subjects with ≥ 50% reduction from the OP in the number of moderate to severe migraine days per month over the entire DBT Phase for the EOD and daily rimegepant dosing regimens relative to placebo.
- 2. To evaluate the mean reduction from the OP in the number of migraine days per month in the last 4 weeks of the DBT Phase for the EOD and daily rimegepant dosing regimens relative to placebo.
- 3. To evaluate the mean reduction from the OP in the number of migraine days per month in the first 4 weeks of the DBT Phase for the EOD and daily rimegepant dosing regimens relative to placebo.
- 4. To evaluate the mean number of acute migraine-specific medication days per month over the entire DBT Phase for the EOD and daily rimegepant dosing regimens relative to placebo.
- 5. To evaluate the mean change from baseline in the Migraine-Specific Quality-of-Life Questionnaire v 2.1 (MSQ) restrictive role function domain score at Week 12 of the DBT Phase for the EOD and daily rimegepant dosing regimens relative to placebo.
- 6. To evaluate the safety and tolerability of rimegepant during the DBT and OLE Phases.

- 7. To evaluate the frequency of alanine aminotransferase (ALT) or aspartate aminotransferase (AST) > 3x upper limit of normal (ULN) concurrent with total bilirubin (TBL) > 2x ULN in subjects treated with rimegepant during the DBT and OLE Phases.
- 8. To evaluate the frequencies of hepatic-related adverse events (AEs) and hepatic-related AEs leading to study drug discontinuation in subjects treated with rimegepant during the DBT and OLE Phases.

3.1.3 Exploratory Objectives

- 1. To evaluate the mean reductions from the OP in the number of migraine days per month and number of headache days per month by pain intensity (total; moderate or severe) in each month and over the entire DBT Phase for the EOD and daily rimegepant dosing regimens relative to placebo.
- 2. To evaluate the proportions of subjects with ≥ 50% reduction, ≥ 75% reduction, and 100% reduction from the OP in the number of migraine days per month and number of headache days per month by pain intensity (total; moderate or severe) in each month and over the entire DBT Phase for the EOD and daily rimegepant dosing regimens relative to placebo.
- 3. To evaluate the mean reductions from the OP in the number of migraine days per week and number of headache days per week by pain intensity (total; moderate or severe) in each week of the first 4 weeks of the DBT Phase for the EOD and daily rimegepant dosing regimens relative to placebo.
- 4. To evaluate the proportions of subjects with ≥ 50% reduction from the OP in the number of migraine days per week and number of headache days per week by pain intensity (total; moderate or severe) in each week of the first 4 weeks of the DBT Phase for the EOD and daily rimegepant dosing regimens relative to placebo.
- 5. To evaluate the proportions of subjects with a migraine day and headache day by pain intensity (total; moderate or severe) on each day of the first week of the DBT Phase for the EOD and daily rimegepant dosing regimens relative to placebo.
- 6. To evaluate the mean number of acute migraine-specific medication days per month in each month and over the entire DBT Phase for the EOD and daily rimegepant dosing regimens relative to placebo.
- 7. To evaluate the mean number of acute migraine medication days per month in each month and over the entire DBT Phase for the EOD and daily rimegepant dosing regimens relative to placebo.
- 8. To evaluate the frequency of liver function test (LFT) elevations (AST, ALT, or TBL) based on fold changes above ULN in subjects treated with rimegepant during the DBT and OLE Phases.

- 9. To evaluate the frequency of ALT or AST > 3x ULN in temporal association with nausea, vomiting, anorexia, abdominal pain or fatigue in subjects treated with rimegepant during the DBT and OLE Phases.
- 10. To evaluate the mean changes from baseline in MSQ domain scores during the DBT and OLE Phases.
- 11. To evaluate the Satisfaction with Medication (SM) scale during the DBT and OLE Phases.
- 12. To evaluate the Clinical Global Impression change (CGI-c) scale during the DBT and OLE Phases.

3.2 Estimands

An estimand is the target of estimation to address the scientific question of interest posed by a study objective. The 4 attributes of an estimand include the population of interest, endpoint of interest, summary of the endpoint, and specification of how intercurrent events are reflected in the scientific question of interest.

For all objectives, the population of interest is defined through appropriate inclusion/exclusion criteria to reflect the targeted patient population for approval. Refer to the protocol for inclusion/exclusion criteria.

Intercurrent Events

Intercurrent events are those that occur after treatment initiation and either preclude observation of the endpoint or affect its interpretation.

Study drug discontinuation before the time point of interest defining the endpoint is considered an intercurrent event.

- For efficacy objectives assessed with a continuous endpoint during the DBT Phase, study drug discontinuation is handled with a "hypothetical strategy," i.e., the hypothetical scenario is that had subjects not discontinued DB study drug, their efficacy would have been similar to the efficacy of subjects from the same treatment group and randomization stratum who did not discontinue DB study drug. All observed values of the endpoint of interest are excluded after DB study drug discontinuation (see Section 7.2), and statistical methods are used to estimate the treatment effect that would have been seen had the intercurrent event not occurred.
- For efficacy objectives assessed with a binary endpoint during the DBT Phase, DB study drug discontinuation is handled with a "composite strategy," i.e., the occurrence of the intercurrent event is integrated as a component of the endpoint. All observed values of the endpoint of interest are excluded after DB study drug discontinuation (see Section 7.2), and subjects with missing data are considered failures.
- For safety objectives, study drug discontinuation is handled with a "while-on-treatment strategy," i.e., response to treatment prior to the occurrence of the intercurrent event of

interest, such that all observed values of the endpoint of interest are used prior to study drug discontinuation plus 7 days (see Section 7.2 and the Core SAP).

• For outcomes research and other objectives, study drug discontinuation is handled with a "treatment policy strategy", i.e., the occurrence of the intercurrent event is considered irrelevant, such that all observed values of the endpoint of interest are used regardless of study drug discontinuation.

Nonstudy prophylactic migraine medication use before the time point of interest defining the endpoint is also considered an intercurrent event. For all objectives, this intercurrent event is handled with a treatment policy strategy, such that all observed values of the endpoint of interest are used. Note that the use of prophylactic migraine medications is prohibited during the study.

Nonstudy acute migraine-specific medication use before the time point of interest defining the endpoint is also considered an intercurrent event, except for efficacy objectives based on acute migraine-specific medication days or acute migraine medication days.

- For efficacy objectives based on migraine days or headache days, this intercurrent event is handled with a composite strategy, such that acute migraine-specific medication use is part of the endpoint definition of migraine days and headache days.
- For safety and outcomes research objectives, this intercurrent event is handled with a treatment policy strategy, such that all observed values of the endpoint of interest are used.

Use of nonstudy other medication to treat headache (migraine or nonmigraine) or aura before the time point of interest defining the endpoint is also considered an intercurrent event, except for the efficacy objective based on acute migraine medication days.

- For efficacy objectives based on headache days, this intercurrent event is handled with a
 composite strategy, such that medication use is part of the endpoint definition of headache
 days.
- For all other efficacy, safety, and outcomes research objectives, this intercurrent event is handled with a treatment policy strategy, such that all observed values of the endpoint of interest are used.

See Section 4.1 for analysis sets that are used to assess endpoints.

Data Sources for Endpoints

Migraine days, acute migraine-specific medication days, acute migraine medication days, headache days, and SM categories are derived from eDiary data from the external source YPrime. Acute migraine-specific medications are triptans and ergotamine. Acute migraine medications are triptans, ergotamine, and other protocol-allowed medications to treat headache (migraine or nonmigraine) or aura, taken on a migraine day.

AEs are determined from AE CRFs.

Grade 3 to 4 laboratory test abnormalities are determined from laboratory test values graded using standardized criteria. Laboratory test results are from an external central laboratory and local laboratory test CRFs.

C-SSRS parameters, MSQ scores, and CGI-c categories are derived from their respective CRFs.

3.2.1 Primary Objective Estimand

The estimand corresponding to the primary endpoint is shown in Table 1.

Table 1 Primary Objective Estimand

| Objective | Mean reduction from the OP in the number of migraine days per month over the entire DBT Phase |
|---------------------|---|
| Efficacy Endpoint | Mean change from the OP in the number of migraine days per month over the entire DBT Phase (Weeks 1 to 12) |
| Summary | Mean change from the OP by treatment group using descriptive statistics and linear mixed effects model with repeated measures, and difference between treatment groups from model for the migraine analysis set |
| Intercurrent Events | Study drug discontinuation: hypothetical strategy Nonstudy prophylactic migraine medication use: treatment policy strategy Nonstudy acute migraine-specific medication use: composite strategy Use of nonstudy other medication to treat headache (migraine or nonmigraine) or aura: treatment policy strategy |

3.2.2 Secondary Objective Estimands

The estimands corresponding to the secondary objectives are shown in Table 2.

Table 2 Secondary Objective Estimands

| Objective 1 | Proportion of subjects with $\geq 50\%$ reduction from the OP in the number of moderate or severe migraine days per month over the entire DBT Phase | |
|---------------------|---|--|
| Efficacy Endpoint | Proportion of subjects with $\geq 50\%$ reduction from the OP in number of moderate or severe migraine days per month over the entire DBT Phase (Weeks 1 to 12) | |
| Summary | Percentage by treatment group and difference in percentages between treatment groups using Mantel-Haenszel risk estimation for the migraine analysis set | |
| Intercurrent Events | Study drug discontinuation: composite strategy | |
| | Nonstudy prophylactic migraine medication use: treatment policy strategy | |
| | Nonstudy acute migraine-specific medication use: composite strategy | |
| | Use of nonstudy other medication to treat headache (migraine or nonmigraine) or aura: treatment policy strategy | |
| Objective 2 | Mean reduction from the OP in the number of migraine days per month in the last 4 weeks of the DBT Phase | |

| Efficacy Endpoint | Mean change from the OP in the number of migraine days per month in the last 4 weeks (Weeks 9 to 12) of the DBT Phase | |
|----------------------------|---|--|
| Summary | Mean change from the OP by treatment group using descriptive statistics and linear mixed effects model with repeated measures, and difference between treatment groups from model for the migraine analysis set | |
| Intercurrent Events | Study drug discontinuation: hypothetical strategy | |
| | Nonstudy prophylactic migraine medication use: treatment policy strategy | |
| | Nonstudy acute migraine-specific medication use: composite strategy | |
| | Use of nonstudy other medication to treat headache (migraine or nonmigraine) or aura: treatment policy strategy | |
| Objective 3 | Mean reduction from the OP in the number of migraine days per month in the first 4 weeks of the DBT Phase | |
| Efficacy Endpoint | Mean change from the OP in the number of migraine days per month in the first 4 weeks (Weeks 1 to 4) of the DBT Phase | |
| Summary | Mean change from the OP by treatment group using descriptive statistics and linear mixed effects model with repeated measures, and difference between treatment groups from model for the migraine analysis set | |
| Intercurrent Events | Study drug discontinuation: hypothetical strategy | |
| | Nonstudy prophylactic migraine medication use: treatment policy strategy | |
| | Nonstudy acute migraine-specific medication use: composite strategy | |
| | Use of nonstudy other medication to treat headache (migraine or nonmigraine) or aura: treatment policy strategy | |
| Objective 4 | Mean number of acute migraine-specific medication days per month over the entire DBT Phase | |
| Efficacy Endpoint | Mean number of acute-migraine-specific days per month on treatment over the entire DBT Phase (Weeks 1 to 12) | |
| Summary | Mean value by treatment group using descriptive statistics and linear mixed effects model with repeated measures, and difference between treatment groups from model for the migraine analysis set | |
| Intercurrent Events | Study drug discontinuation: hypothetical strategy | |
| | Nonstudy prophylactic migraine medication use: treatment policy strategy | |
| | Nonstudy acute migraine-specific medication use: not applicable | |
| | Use of nonstudy other medication to treat headache (migraine or nonmigraine) or aura: treatment policy strategy | |
| Objective 5 | Mean change from baseline in the MSQ restrictive role function domain score at Week 12 of the DBT Phase | |
| Outcomes Research | Mean change from baseline in the MSQ restrictive role function domain score at Week 12 of the DBT Phase | |
| Endpoint | Week 12 of the DBT Phase | |
| Endpoint Summary | Mean change from baseline by treatment group using descriptive statistics and linear regression model, and difference between treatment groups from model for the DBT efficacy analysis set | |
| _ | Mean change from baseline by treatment group using descriptive statistics and linear regression model, and difference between treatment groups from model for the DBT | |

| | Nonstudy acute migraine-specific medication use: treatment policy strategy Use of nonstudy other medication to treat headache (migraine or nonmigraine) or aura: treatment policy strategy | | |
|----------------------------|--|--|--|
| Objective 6 | Safety and tolerability of rimegepant during the DBT and OLE Phases | | |
| Safety Endpoint | Number and percentage of subjects with AEs by intensity, serious adverse events (SAEs), AEs leading to study drug discontinuation, and grade 3 to 4 laboratory test abnormalities on treatment | | |
| Summary | AEs: Frequency by treatment group for the DBT and OL rimegepant safety analysis sets | | |
| | Laboratory test abnormalities: Frequency by treatment group for the DBT and OL rimegepant safety analysis sets with laboratory test data on treatment | | |
| Intercurrent Events | Study drug discontinuation: while-on-treatment strategy | | |
| | Nonstudy prophylactic migraine medication use: treatment policy strategy | | |
| | Nonstudy acute migraine-specific medication use: treatment policy strategy | | |
| | Use of nonstudy other medication to treat headache (migraine or nonmigraine) or aura: treatment policy strategy | | |
| Objective 7 | Frequency of ALT or AST $> 3x$ ULN concurrent with TBL $> 2x$ ULN in subjects treated with rimegepant during the DBT and OLE Phases | | |
| Safety Endpoint | Number and percentage of subjects with AST or ALT $> 3x$ ULN concurrent (i.e., on the same laboratory collection date) with TBL $> 2x$ ULN on treatment | | |
| Summary | Frequency by treatment group for the DBT and OL rimegepant safety analysis sets with LFT data on treatment | | |
| Intercurrent Events | Study drug discontinuation: while-on-treatment strategy | | |
| | Nonstudy prophylactic migraine medication use: treatment policy strategy | | |
| | Nonstudy acute migraine-specific medication use: treatment policy strategy | | |
| | Use of nonstudy other medication to treat headache (migraine or nonmigraine) or aura: treatment policy strategy | | |
| Objective 8 | Frequencies of hepatic-related AEs and hepatic-related AEs leading to study drug discontinuation in subjects treated with rimegepant during the DBT and OLE Phases | | |
| Safety Endpoint | Number and percentage of subjects with hepatic-related AEs and hepatic-related AEs leading to study drug discontinuation on treatment | | |
| Summary | Frequency by treatment group for the DBT and OL rimegepant safety analysis sets | | |
| Intercurrent Events | Study drug discontinuation: while-on-treatment strategy | | |
| | Nonstudy prophylactic migraine medication use: treatment policy strategy | | |
| | Nonstudy acute migraine-specific medication use: treatment policy strategy | | |
| | Use of nonstudy other medication to treat headache (migraine or nonmigraine) or aura: treatment policy strategy | | |

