2.2 Secondary

- To evaluate the proportion of subjects with ≥ 50% reduction from the Observation Phase in the number of moderate to severe migraine days per month over the entire Double-blind Treatment Phase for the EOD and daily rimegepant dosing regimens relative to placebo.
- To evaluate the mean reduction from the Observation Phase in the number of migraine days per month in the last 4 weeks of the Double-blind Treatment Phase for the EOD and daily rimegepant dosing regimens relative to placebo.
- To evaluate the mean reduction from the Observation Phase in the number of migraine days per month in the first 4 weeks of the Double-blind Treatment Phase for the EOD and daily rimegepant dosing regimens relative to placebo.
- To evaluate the mean number of acute migraine-specific medication days per month over the
 entire Double-blind Treatment Phase for the EOD and daily rimegepant dosing regimens
 relative to placebo.
- To evaluate the mean change from baseline in the Migraine-Specific Quality-of-Life
 Questionnaire v 2.1 (MSQ) restrictive role function domain score at Week 12 of the Doubleblind Treatment Phase for the EOD and daily rimegepant dosing regimens relative to
 placebo.
- To evaluate the safety and tolerability of rimegepant during the Double-blind Treatment and Open-label Extension Phases.
- To evaluate the frequency of ALT or AST > 3x upper limit of normal (ULN) concurrent with total bilirubin > 2x ULN in subjects treated with rimegepant during the Double-blind Treatment and Open-label Extension Phases.

To evaluate the frequencies of hepatic-related adverse events (AEs) and hepatic-related AEs
leading to study drug discontinuation in subjects treated with rimegepant during the Doubleblind Treatment and Open-label Extension Phases.

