3.2 Secondary

- Proportion of subjects with ≥ 50% reduction from the Observation Phase in the number of moderate to severe migraine days per month over the entire Double-blind Treatment Phase (Weeks 1 to 12).
- Mean change from the Observation Phase in the number of migraine days per month in the last 4 weeks (Weeks 9 to 12) of the Double-blind Treatment Phase.
- Mean change from the Observation Phase in the number of migraine days per month in the first 4 weeks (Weeks 1 to 4) of the Double-blind Treatment Phase.
- Mean number of acute migraine-specific medication days per month over the entire Doubleblind Treatment Phase (Weeks 1 to 12). Acute migraine-specific medications are triptans and ergotamine (see Section 3.3).
- Mean change from baseline in the MSQ restrictive role function domain score at Week 12 of the Double-blind Treatment Phase.

- Number and percentage of subjects with AEs by intensity, serious adverse events (SAEs), AEs leading to study drug discontinuation, and grade 3 to 4 laboratory test abnormalities during the Double-blind Treatment and Open-label Extension Phases.
- Number and percentage of subjects treated with rimegepant with AST or ALT elevations >
 3x ULN concurrent (i.e., on the same laboratory collection date) with total bilirubin > 2x
 ULN during the Double-blind Treatment and Open-label Extension Phases.
- Number and percentage of subjects treated with rimegepant with hepatic-related AEs by intensity, and hepatic-related AEs leading to study drug discontinuation during the Doubleblind Treatment and Open-label Extension Phases.

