9.3.2 Safety Analyses

Deaths will be listed regardless of onset for the enrolled analysis set.

The frequencies of safety endpoints will be assessed descriptively as the number and percentage of subjects with events/findings separately for the 3 safety analysis sets.

The frequencies of the following safety endpoints will be tabulated on treatment: AEs by intensity (mild, moderate, severe, total); AEs by relationship to study drug (related, possibly related, unlikely related, not related); SAEs; AEs leading to study drug discontinuation; hepatic-related AEs by intensity; hepatic-related AEs leading to study drug discontinuation; laboratory test abnormalities by toxicity grade; and LFT elevations based on fold changes above ULN, including ALT or AST > 3x ULN concurrent (on the same laboratory test collection date) with total bilirubin > 2x ULN.

The investigators will determine the intensity of AEs and the relationship of AEs to study drug. The investigators' terms will be coded using the latest version of the Medical Dictionary for Regulatory Activities (MedDRA). AEs will be tabulated by system organ class and preferred term. In tables by intensity, if a subject has an AE with different intensities over time, then only the greatest intensity will be reported. In tables by relationship to study drug, if a subject has an AE with different relationships over time, then the highest degree of relatedness to study drug will be reported.

Laboratory test results will be graded according to numeric laboratory test criteria in Common Terminology Criteria for Adverse Events (CTCAE) Version 5.0 (2017), if available. Otherwise, if CTCAE grades are not available, then results will be graded according to numeric laboratory test criteria in Division of AIDS (DAIDS) Table for Grading the Severity of Adult and Pediatric Adverse Events Corrected Version 2.1 (2017). If a subject has a laboratory test abnormality with different toxicity grades over time, then only the highest toxicity grade will be reported.

In addition, Quality Tolerance Limits (QTLs) are predefined parameters that are monitored during the study. Important deviations from the QTLs and any remedial actions taken will be summarized.

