6.4.1.3 On-DBT AEs

Frequency tables of on-DBT AEs are provided for the DBT safety analysis set by SOC and PT for the following endpoints:

- AEs by worst intensity (secondary objective #6)
- AEs related to study drug by worst intensity
- SAEs (secondary objective #6)
- AEs leading to study drug discontinuation
- Hepatic-related AEs (secondary objective #8)
- Hepatic-related AEs leading to study drug discontinuation
- Potential drug abuse AEs, displayed in alphabetical order by intensity and PT without SOC
- Cardiovascular AEs
- Suicidality AEs
- Hypertension AEs
- Hypertension AEs for subjects with medical history of hypertension.

Frequency tables of AEs by SOC and PT display AEs in descending order of rimegepant QD frequency within SOC and PT, unless otherwise specified.

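### The SAP's hepatic adverse event endpoint and tables omit the intensity breakdown that the protocol specifies, and no change is recorded

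*SAP*

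**What the plan says.** The protocol asks for intensity. Section 3.2 defines the endpoint as "Number and percentage of subjects treated with rimegepant with hepatic-related AEs by intensity, and hepatic-related AEs leading to study drug discontinuation", in both the double-blind and open-label phases, and the synopsis lists it the same way. The safety analyses in Section 9.3.2 repeat it among the planned tabulations: "hepatic-related AEs by intensity; hepatic-related AEs leading to study drug discontinuation". The objective behind the endpoint, in Section 2.2, is looser and speaks only of frequency: "To evaluate the frequencies of hepatic-related adverse events (AEs) and hepatic-related AEs".

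The SAP does not carry intensity over. Table 2 in Section 3.2.2, Objective 8, has "Number and percentage of subjects with hepatic-related AEs and hepatic-related AEs leading to study drug discontinuation on treatment". The double-blind table list in Section 6.4.1.3 has "Hepatic-related AEs (secondary objective #8", with no intensity. The open-label list in Section 6.4.1.4 plans the same two hepatic tables, again without intensity, and assigns both to exploratory objective 10.

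**The concern.** The two documents define one secondary safety endpoint differently. Followed exactly, the SAP gives the number of subjects with any hepatic event but not how many had a mild, moderate or severe event as their worst. That split is the part the protocol adds beyond a simple count.

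The liver is where a reader will look first. Protocol Section 1.3 treats possible liver test elevation as the main identified adverse event of interest, and Section 10.2 says there is no data monitoring committee. The daily arm takes 75 mg a day. SAP Section 6.2.6.1 codes the every-other-day arm at 37.5 mg a day, so the daily arm has 75 / 37.5 = 2 times the average dose. A severity profile of hepatic events by arm is therefore worth having in the form the protocol set out.

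**Working it through.** There is no figure in the plan to reproduce. The check is a comparison of text, followed by a test of whether another planned output supplies the missing count.

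**Step 1. Compare the two components of the endpoint, place by place.**

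| Place | Hepatic events | Hepatic events leading to discontinuation |
|---|---|---|
| Protocol 2.2 (objective) | frequency only | yes |
| Protocol 3.2 and synopsis (endpoint) | by intensity | yes |
| Protocol 9.3.2 (analysis) | by intensity | yes |
| SAP 3.1.2 (objective 8) | frequency only | yes |
| SAP Table 2, Objective 8 (endpoint) | frequency only | yes |
| SAP 6.4.1.2 (overview) | frequency only | yes |
| SAP 6.4.1.3 (double-blind tables) | frequency only | yes |
| SAP 6.4.1.4 (open-label tables) | frequency only | yes |
| SAP 6.4.1.5 (combined rimegepant tables) | not listed | not listed |

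The objectives agree with each other and the discontinuation component agrees throughout. The difference is confined to the intensity split of the first component.

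**Step 2. Is the SAP wording shorthand?** It does not read that way. Table 2 keeps intensity for Objective 6: "Number and percentage of subjects with AEs by intensity, serious adverse events (SAEs), AEs leading to study drug discontinuation". The lists in 6.4.1.3 and 6.4.1.4 name intensity for all adverse events, for related adverse events and for potential drug abuse events. The SAP states intensity where it wants it, and the hepatic lines lack it.

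**Step 3. Is it a recorded decision?** SAP Section 2.4 lists the protocol changes that affected analyses, and this is not one of them. The revision history entries for Table 2 that touch Objective 8 concern its intercurrent events row and its summary row, not its endpoint row. No entry for the adverse event sections removes hepatic intensity.

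**Step 4. Does another listed output give the count?**

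- All adverse events are tabulated by worst intensity within system organ class and preferred term. That shows the intensity of each hepatic term. It does not give subjects by worst hepatic intensity, because one subject can appear under several terms. As an illustration, take a subject with one mild and one moderate hepatic term. Summing rows counts 1 mild + 1 moderate = 2, but the correct entry is 1 subject, moderate.
- A system organ class row would serve only if the hepatic grouping coincided with a single class. Nothing in these documents says so.
- The overview table has no intensity split.
- The by-subject listing is raw data, whereas the endpoint is a number and percentage of subjects.

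**Step 5. Objective tags.** In SAP Section 3.1.3, exploratory objective 10 concerns the Migraine-Specific Quality-of-Life domain scores, and Section 6.5.1 uses the tag in that sense. Hepatic events are secondary objective 8 in Section 3.1.2. The tag on the two open-label hepatic tables is therefore wrong.

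**The case against.** A reader might infer that the protocol's endpoint has been dropped and will not be produced. The documents do not support that. Both hepatic components are planned for both treatment phases, and together they answer the objective as worded, which asks only for frequencies. In addition, SAP Section 6.4.1 leaves the contents of adverse event outputs to the Core SAP, and Section 6.1.1 leaves templates to a separate mock document. Neither is available here, and either could include an intensity column. The supportable statement is that this SAP does not specify the breakdown. This objection stands, and it limits the point to that.

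It does not remove the point. Table 2 is where the study's SAP defines the endpoint, and that definition differs from Protocol Section 3.2 whatever the unseen documents contain.

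The other fair objection is that liver severity is well covered elsewhere. The SAP plans concurrent transaminase and bilirubin elevations, elevation and shift tables, time to first elevation, eDISH plots, worst laboratory abnormalities, separate tables of serious events, and narrative identification for terms such as hepatic failure and jaundice. This also stands, and it is why the point is small. These outputs describe laboratory values, seriousness or individual cases. None of them is the count of subjects by worst intensity of a hepatic adverse event.

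**Conclusion.** The concern holds in a narrow form. The SAP omits, without recording a change, the intensity breakdown of one of the two components of one of the protocol's three secondary safety endpoints. The omission runs through Table 2 and the table lists for both the double-blind and open-label phases.

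A reader might also infer that the planned hepatic tables blur mild enzyme findings with serious liver events. They do so only in the group total, because they are laid out by system organ class and preferred term, so different kinds of hepatic event appear on separate rows.

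There is no inferential consequence. SAP Section 5 says that secondary safety endpoints are not tested, and the protocol assesses them descriptively, so type 1 error and power are unchanged. The conclusion assumes that the hepatic grouping is not the same as a single system organ class. It makes no assumption about what the Core SAP or the mock tables contain. This is a desirable correction and does not threaten the trial's conclusions.

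**What to change.** In SAP Table 2 (Objective 8), Section 6.4.1.3 and Section 6.4.1.4, change the hepatic entry to *hepatic-related AEs by worst intensity*. Worst intensity is the right reading of the protocol, because Section 9.3.2 reports only the greatest intensity when an event varies over time. In Section 6.4.1.4, change the tag on both hepatic tables from exploratory objective 10 to secondary objective 8. If the sponsor prefers to leave intensity out, the SAP should record that as a departure from the protocol and give the reason.

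The cost is a few words in three places. The investigators already grade the intensity of every adverse event, and the SAP already plans worst-intensity tables for all adverse events, so no new data are needed.
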